For the RCT comparing NDURE to usual care, we note that our accrual rate target of 60%, by which we establish the feasibility of recruitment for this RCT, will have been tested in the pilot single-arm feasibility study. Refinements to the recruitment strategies and study timeline, as described below, will occur as needed to ensure that we achieve our accrual targets described below. We propose to accrue 75 patients to each arm (white, n=50 and AA, n=25) to the study over 36 months. Based on data from MUSC/HCC for 2018, it is expected that 125 patients/year will be eligible for the study, of whom 28 (22%) are expected to be AA and 97 (78%) are expected to be white. During the 36-month accrual period, we would expect to screen 375 patients, of whom 83 would be AA and 292 would be white. Based on the PI and study team's prior experience recruiting and enrolling for similar studies embedded into clinical care and the feasibility data gathered from the single-arm pilot of NDURE, we anticipate that 60% of eligible patients will accrue to this study. Based on this 60% accrual rate, over the course of 36 months, we would expect to accrue 225 patients (50 AAs and 175 white). Thus, by conservative estimates with appropriate over-sampling of AAs, our overall accrual target (n=150) and for the AA racial subgroup (n=50) appear highly feasible. If continued optimization of enrollment and recruitment strategies fails to yield an accrual rate of 60%, we will extend the duration of the study accrual beyond the planned 36 months by an additional 6 months (and remain within the grant funding period). If we extend the study timeline for accrual by 6 months to 42 months instead of 36 months (and thus screen 437 patients [96 AAs] instead of 375 [83 AAs]), we would only need an accrual rate of 52% among AAs to achieve our racial subgroup distribution of n=50 (and an accrual rate of 29% among white HNSCC patients). For all of the above reasons (PI and team experience, feasibility testing, refinement of recruitment protocols, and extension of recruitment period), we are highly confident that we can accrue our overall and racial subgroup targets for the RCT.

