9.1.2 RCT OF NDURE VERSUS USUAL CARE

PORT Delay (Primary Endpoint)

We hypothesize that, compared with patients who receive usual care, patients who receive NDURE will have a decreased rate of PORT delay (initiation of PORT > 6 weeks after surgery). Alternatively, our null hypothesis is that there will be no difference in the rate of PORT delay between NDURE and usual care.

PORT Delay (Secondary Endpoint)

We hypothesize that, compared with usual care, NDURE will result in a smaller difference in the rate of PORT delay (initiation of PORT > 6 weeks after surgery) between AA and white patients. Alternatively, our null hypothesis is that there will be no difference in the rate of PORT delay between AA and white patients between NDURE and usual care.

TTP (Secondary Endpoint)

We hypothesize that, compared with patients who receive usual care, patients who receive NDURE will have a shorter median TTP (time, in days, between the date of definitive surgical resection to the initiation of PORT). Alternatively, our null hypothesis is that there will be no difference in median TTP between NDURE and usual care.

TTP (Secondary Endpoint)

We hypothesize that, compared with usual care, NDURE will result in a smaller difference in the median TTP between AA and white patients. Alternatively, our null hypothesis is that there will be no difference in the median TTP between AA and white patients between NDURE and usual care.

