9.4.4.2 RCT OF NDURE VERSUS USUAL CARE

PORT delay disparity (Black vs White) in NDURE vs UC: The comparison of PORT delay disparity (PORT delay in Black patients vs PORT delay in White patients) in NDURE versus UC will be evaluated using a similar GLM as described for the primary endpoint, but the model will include a race-by-treatment

arm interaction term. Model-based estimates of PORT delay disparity will be constructed for each arm with corresponding 90% CIs. The model-based difference in disparity between trial arms will be reported along with corresponding 90% CIs. Analysis will be performed using the PORT delay analysis set.

Time-to-PORT initiation, NDURE vs UC: TTP will be analyzed using cumulative incidence plots (1 – Kaplan-Meier plots) with Greenwood variance estimation to construct corresponding 90% CIs. Treatment group comparisons will be conducted using a stratified log-rank test adjusting for randomization stratification variables. As noted, TTP will be right-censored for evaluable patients who die or are lost to follow-up prior to PORT initiation, or who haven't received PORT by the end of follow-up (18 weeks post-operatively). The hazard ratio comparing the two arms will be estimated using Cox proportional hazards regression controlling for stratification variables. A sensitivity analysis will be conducted treating deaths prior to PORT initiation as a competing risk to evaluate the bias incurred in cumulative incidence estimation by right-censoring deaths. Analyses will be performed using the TTP analysis set.

Time-to-PORT initiation (Black vs White) in NDURE vs UC: TTP cumulative incidence plots (1 – Kaplan-Meier plots) will be constructed for Black and White patients randomized to NDURE and for Black and White patients randomized to UC as described. Group comparisons will be conducted using a stratified log-rank test, but controlling only for predicted radiation facility as a randomization stratification variable since a race-by-trial arm interaction term is used to evaluate this hypothesis. A Cox proportional hazards regression model will be fit as described with appropriate race-by-trial arm interaction. Censoring rules will be as described in Section 9.4.2. A sensitivity analysis will be performed treating deaths prior to PORT initiation as a competing risk. Analyses will be conducted using the TTP analysis set.

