Treatment package time, NDURE vs UC: TPT is defined as the number of days between the date of definitive surgery and the date of PORT completion. Analysis will be conducted using cumulative incidence plots (1 – Kaplan-Meier plots) with Greenwood variance estimation to construct corresponding 90% CIs. Treatment group comparisons will be conducted using a stratified log-rank test adjusting for randomization stratification variables. TPT will be right-censored as described in Section 9.4.2. The hazard ratio comparing the two arms will be estimated using Cox proportional hazards regression controlling for stratification variables. A sensitivity analysis will be conducted treating deaths after PORT initiation but prior to the completion of PORT as a competing risk to evaluate the bias incurred in cumulative incidence estimation by right-censoring deaths. Analyses will be performed using the TPT analysis set.

Treatment package time (Black vs White) in NDURE vs UC: TPT cumulative incidence plots (1 – Kaplan-Meier plots) will be constructed for Black and White patients randomized to NDURE and for Black and White patients randomized to UC as described. Group comparisons will be conducted using a stratified log-rank test, but controlling only for predicted radiation facility as a randomization stratification variable since a race-by-trial arm interaction term is used to evaluate this hypothesis. A Cox proportional hazards regression model will be fit as described with appropriate race-by-trial arm interaction. Censoring rules will be as described in Section 9.4.2. A sensitivity analysis will be performed treating deaths after PORT initiation but prior to the completion of PORT as a competing risk. Analyses will be conducted using the TPT analysis set.

Time from surgery to PORT referral scheduling, NDURE vs UC: Time from surgery to PORT referral scheduling will be analyzed using the approach described for all time-to-event endpoints. Censoring rules will be as described in Section 9.4.2. Analyses will be performed using the time from surgery to PORT referral scheduling analysis set.

Time from surgery to appointment with radiation oncology, NDURE vs UC: Time from surgery to appointment with radiation oncology will be analyzed using the approach described for all time-to-event endpoints. Censoring rules will be as described in Section 9.4.2. Analyses will be performed using the time from surgery to appointment with radiation oncology analysis set.

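### The TTP and TPT racial-disparity analyses add a log-rank comparison of undefined groups that does not test a difference in disparity, and the plan does not commit to reporting the Cox interaction that does

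*Combined protocol and SAP*

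**What the plan says.** Section 9.1.2 gives the TTP disparity hypothesis as a between-arm contrast of a between-race difference: compared with usual care, "NDURE will result in a smaller difference in the median TTP between AA and white patients". It has no matching hypothesis for TPT. Table 2 lists TPT, with PORT delay and TTP, under the racial-disparity secondary objective.

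Section 9.4.4.2 treats the two endpoints in near-identical paragraphs:

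- **Plots.** Cumulative incidence curves are "constructed for Black and White patients randomized to NDURE and for Black and White patients randomized to UC as described", which makes four curves.
- **Log-rank.** "Group comparisons will be conducted using a stratified log-rank test, but controlling only for predicted radiation facility as a randomization stratification variable". The groups and the degrees of freedom are not given.
- **Reason given.** The sentence ends "since a race-by-trial arm interaction term is used to evaluate this hypothesis".
- **Model.** "A Cox proportional hazards regression model will be fit as described with appropriate race-by-trial arm interaction".

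The binary PORT-delay disparity paragraph in the same section uses only an interaction model and ends with a reporting commitment: "The model-based difference in disparity between trial arms will be reported along with corresponding 90% CIs". The TTP and TPT disparity paragraphs have no such commitment.

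**The concern.** Whether the racial gap is smaller under NDURE is a race-by-arm interaction. A log-rank test has no interaction term, and neither natural reading of the group comparisons supplies one:

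- **All four race-by-arm groups.** This is a 3-df test of whether any curve differs from the others. It rejects if NDURE helps both races equally, or if a racial gap exists and NDURE leaves it alone.
- **Black versus White within each arm.** This gives two p-values, neither of which tests whether the gaps differ. It invites an inference from significance in usual care and non-significance in NDURE.

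At stake is which p-value is reported as the disparity result. In the overall TTP and TPT paragraphs the log-rank does the testing and Cox regression supplies the estimate. The disparity paragraphs follow the same layout and do not say that the interaction result decides. A small log-rank p-value beside a non-significant interaction is a likely outcome, and the plan has no rule for it.

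**Working it through.** **1. Inputs from the documents.** 75 patients per arm, 50 white and 25 AA (Section 5.5). Delay rates 45% versus 25% at two-sided alpha 0.10 (Section 9.2.2). Section 9.4.1 gives 0.05 with 90% CIs as the general rule, so both levels are shown. TTP is censored at day 126 (Section 8.4.4).

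**2. The plan's own figure.** No power is stated for any disparity hypothesis. The stated 83% for the primary comparison reproduces:

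- SE under the null = √(2 × 0.35 × 0.65 / 75) = 0.0779
- SE under the alternative = √((0.45 × 0.55 + 0.25 × 0.75) / 75) = 0.0762
- Power = Φ((0.20 − 1.645 × 0.0779) / 0.0762) = Φ(0.94) = 82.7%

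**3. Assumptions not in the documents.**

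- Proportional hazards, Weibull shape 4.
- 45% of white usual-care patients in the reference facility stratum not started at day 42.
- Full-effect arm HR for starting PORT = ln(0.25)/ln(0.45) = 1.74; a weaker 1.3 is also run.
- AA-versus-white HR 0.75, or 0.6 as an alternative.
- Facility HR 0.8, 50:50 split.
- Censoring at day 126 only.

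**4. Four-group reading.** There were 3,000 simulated trials per row. The facility-stratified 3-df log-rank is set against the Wald test of the race-by-arm term in a facility-stratified Cox model. The race HR is the same in both arms, so every interaction rejection is a false positive.

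| Arm HR | Race HR | Log-rank, α 0.10 | Interaction, α 0.10 | Log-rank, α 0.05 | Interaction, α 0.05 |
|---|---|---|---|---|---|
| 1 | 1 | 12% | 11% | 6% | 5% |
| 1 | 0.75 | 36% | 12% | 24% | 5% |
| 1.3 | 0.75 | 56% | 11% | 44% | 5% |
| 1.74 | 1 | 87% | 11% | 79% | 6% |
| 1.74 | 0.75 | 94% | 11% | 87% | 6% |

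A separate run of 1,000 trials with facility HR 0.7 and arm HR 1.74 gave log-rank rejection of 92% (race HR 0.75) and 87% (race HR 1), against 11.5% and 10.0% for the interaction.

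**5. Within-arm reading.** If nearly all patients start PORT, the SE of the log race HR in one arm is √(1/25 + 1/50) = 0.245. At race HR 0.75, |ln 0.75| / 0.245 = 1.17, so each arm's test has about 32% power at alpha 0.10. The chance that usual care is significant and NDURE is not, with identical disparity, is 0.32 × 0.68 = 22%. Simulation gave 21 to 22%.

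**6. What the interaction can show.** If NDURE fully removes the disparity at arm HR 1.74, interaction power at alpha 0.10 is 22% (race HR 0.75) to 42% (race HR 0.6). With all 150 patients having events, the SE of the log ratio of hazard ratios is √(2/25 + 2/50) = 0.346. Then 80% power needs a ratio of exp((1.645 + 0.842) × 0.346) = 2.4.

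**7. Scale.** Equal hazard ratios do not mean equal median gaps. Under the assumptions in step 3 (reference facility, race HR 0.75):

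- White usual-care median = 42 × (ln 2 / −ln 0.45)^(1/4) = 40.5 days
- Usual-care gap = 40.5 × (0.75^(−1/4) − 1) = 3.0 days
- NDURE gap = 3.0 × 1.74^(−1/4) = 3.0 × 0.87 = 2.6 days

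The median gap narrows by about 13% with no interaction on the hazard scale.

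**The case against.** The strongest reply is that the plan already names the right test. The log-rank sentence ends "since a race-by-trial arm interaction term is used to evaluate this hypothesis", and the Cox model with that interaction follows at once. A reader who stops at the log-rank might infer that it is the only test given to these hypotheses, or that they have no valid test. The documents do not support either inference.

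The since-clause can also be read as explaining why race is dropped from the strata, given that race is now part of the comparison. It need not claim that a log-rank test contains an interaction. That is a fair reading. It still leaves open which groups are compared and what their p-value is for.

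The four-group test is itself inferred. It is the natural reading of four plotted curves, but it is not written. The rejection rates in step 4 apply to that reading alone.

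A reader might also infer that the log-rank would almost always reject. That needs the full targeted effect: at arm HR 1.3 and race HR 0.75 the rate is 56% at alpha 0.10 and 44% at 0.05.

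Finally, these are secondary analyses in a pilot trial, and the binary disparity analysis is already properly specified. That limits the consequence, but the prescribed comparison still does not answer the question of its own paragraph.

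**Conclusion.** The point holds as a misplaced companion test with no precedence rule. Both paragraphs prescribe a log-rank comparison that, on either natural reading, does not test whether the disparity differs between arms. Neither commits to reporting the interaction estimate with a CI.

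With equal race hazard ratios in both arms, the four-group log-rank rejects in about 55% (arm HR 1.3, race HR 0.75) to about 90% (arm HR 1.74) of simulated trials at alpha 0.10. The interaction rejects in 11 to 12%. The exact rates rest on the assumptions in step 3. That a global test responds to arm and race main effects does not.

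The simulation is for TTP at the planned sizes. TPT was not simulated separately: its paragraph has the same structure, and its analysis set is limited to patients who started PORT. The median-scale mismatch concerns TTP, the only time-to-event disparity hypothesis in Section 9.1.2.

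**What to change.** In both Black-versus-White paragraphs of Section 9.4.4.2 (TTP and TPT):

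1. Delete the log-rank sentence, or label the four-curve comparison descriptive with no p-value.
2. State that the disparity inference rests only on the race-by-arm term of the Cox model. Report it as a ratio of hazard ratios (AA versus white in NDURE, divided by AA versus white in usual care) with 90% CI and p-value, in line with the binary PORT-delay disparity paragraph.
3. For TTP, either reword the Section 9.1.2 disparity hypothesis on the hazard-ratio scale, or keep the medians and report the between-arm difference in the Black-White median gap with a 90% CI.

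The cost is wording. The interaction model is already planned and no further data or patients are needed. The median option in item 3 adds one estimate and its interval.

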trial arms will be analyzed using a model-based approach (discussed in Section 9.4.3.2) with inclusion of randomization stratification variables as model covariates, an analytic approach which preserves the type I error rate at nominal α , and increases power relative to an unadjusted model.⁶¹ Therefore, our power analysis based on a Z-test is conservative, and we anticipate even greater power based on our analytic plan. We therefore consider our RCT to be appropriately and rigorously designed to detect a clinically meaningful reduction in PORT delay. In order to have 150 patients eligible for the PORT delay analysis set (see Section 9.3, Population for Analyses), we plan to enroll 170 patients. Our sample size is inflated by 17% based on historical data. If at 170 patient accruals we have not achieved 75 patients evaluable for the primary endpoint in each arm, we will continue to enroll until we have achieved either accrual of a minimum of 75 evaluable patients in each arm or have accrued a maximum of 180 total patients.

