9.4.3.2 RCT OF NDURE VERSUS USUAL CARE

For the primary endpoint (delays starting PORT as defined in **Section 8.4, Endpoint and Other Non-Safety Assessments**), the difference in PORT delay comparing NDURE to UC will be evaluated using a model-based approach to accommodate adjustment for randomization stratification variables. Specifically, we will use a binary regression generalized linear model (GLM) with identity link to model the probability of PORT delay as a function of treatment arm and randomization stratification variables (race and predicted location of radiation facility). We adopt this approach as opposed to a logit model or Mantel-Haenzel (MH) type approach since the estimand is the population average treatment effect, whereas the odds ratio is not collapsable and therefore inference based on logistic regression or MH estimation would be limited to a conditional treatment effect. (Additional details can be found in the FDA Guidance Document on Adjusting for Covariates in Randomized Clinical Trials.) The risk difference (PORT delay rate in UC – PORT delay rate in NDURE) will be estimated based on the treatment effect slope parameter. We will report the corresponding model-based 90% CI and two-sided p-value. We will additionally report model-based PORT delay rates for each trial arm with corresponding 90% CIs. Should GLM convergence be an issue, we will adopt an alternative approach based on subject-level predicted probabilities of PORT delay from a logistic model as outlined by Freedman⁶² and by Steingrimsson.⁶³ Analysis will be performed using the PORT delay analysis set.

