Pre-surgical radiation consultation, NDURE vs UC: will be analyzed using a binary regression GLM with identity link as described. If the GLM fails to converge, then unadjusted (empirical) rates and corresponding 90% CIs will be constructed, with trial-arm comparisons conducted using a z-test of two independent proportions. Analyses will be performed using the FAS.

Dental evaluation prior to surgery, NDURE vs UC: will be analyzed using a binary regression GLM with identity link as described. If the GLM fails to converge, then unadjusted (empirical) rates and corresponding 90% CIs will be constructed, with trial-arm comparisons conducted using a z-test of two independent proportions. Analyses will be performed using the dental evaluation prior to surgery analysis set.

Extraction of indicated teeth, NDURE vs UC: will be analyzed using a binary regression GLM with identity link as described. If the GLM fails to converge, then unadjusted (empirical) rates and corresponding 90% CIs will be constructed, with trial-arm comparisons conducted using a z-test of two independent proportions. Analyses will be performed using the extraction of indicated teeth analysis set.

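### Three care-process endpoints lose stratum adjustment if the identity-link model fails, while the primary endpoint keeps it: a minor inconsistency that costs almost nothing to remove

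*Combined protocol and SAP*

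**What the plan says.** Each of the three care-process endpoints in Section 9.4.4.2 (pre-surgical radiation consultation, dental evaluation prior to surgery, extraction of indicated teeth) "will be analyzed using a binary regression GLM with identity link as described". The reference is to the primary model in Section 9.4.3.2, which contains arm, race and predicted radiation facility. For all three the fallback first changes the estimates: "If the GLM fails to converge, then unadjusted (empirical) rates and corresponding 90% CIs will be constructed". The test then carries no covariates either, since the plan has "trial-arm comparisons conducted using a z-test of two independent proportions".

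For the primary endpoint, Section 9.4.3.2 says: "Should GLM convergence be an issue, we will adopt an alternative approach based on subject-level predicted probabilities of PORT delay from a logistic model". That route stays adjusted and keeps a risk difference. The identity link was chosen there "since the estimand is the population average treatment effect". Section 9.2.2 adds that including the stratification variables "increases power relative to an unadjusted model".

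PORT delay disparity, another secondary binary analysis in Section 9.4.4.2, uses a model like the primary one and has no z-test fallback. Dental evaluation has an analysis in Section 9.4.4.2 but is not listed among the endpoints in Table 2.

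**The concern.** The same model has two different rescue routes, and the route for the care-process endpoints discards an adjustment that the plan itself credits with extra power. An identity-link binomial model is most fragile when fitted probabilities approach 1. These are processes that the navigator is assigned to bring about (Section 6.1.1.1, Function 6), and the extraction set is a subset of a subset of the full analysis set (Section 9.3), so a failed fit is a realistic possibility.

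Two things are at stake. One is some precision on these endpoints. The other is that adjustment would hinge on a software event that the plan does not define: failure to converge has no stated criterion, and programs differ in how they treat fitted probabilities outside 0–1.

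**Working it through.** **1. The plan's own figure.** Section 9.2.2 states 83% power for 45% versus 25%, 75 per arm, two-sided alpha 0.10, pooled z-test. With p̄ = 0.35:
- null SE = √(2 × 0.35 × 0.65 / 75) = 0.0779; × 1.645 = 0.1281
- alternative SE = √((0.45 × 0.55 + 0.25 × 0.75) / 75) = 0.0762
- power = Φ((0.20 − 0.1281) / 0.0762) = Φ(0.944) = 82.7%

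The figure reproduces. It concerns the primary endpoint; the plan has no corresponding calculation for the care-process endpoints.

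**2. Inputs.** From the documents: 1:1 allocation and one third AA (Section 6.3), 170 planned (Section 9.2.2). Assumed, because the documents are silent: 50% predicted non-MUSC; NDURE rates 70–95% and usual-care rates 45–60%; a small subset of N = 60; log-odds stratum effects of none, moderate (race −0.5, facility −1.0) or strong (race −0.5, facility −2.0).

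**3. Precision lost by dropping the strata.** Let T be the sum over arms of p(1 − p), W the sum over arms of the average within-stratum p(1 − p), and V the between-stratum variance of the risk difference. In large samples the ratio of unadjusted to adjusted SE is √(2T / (2W + V)). For 45% versus 70%, T = 0.2475 + 0.2100 = 0.4575.
- Moderate: W = 0.4277, V = 0.0006; √(0.9150 / 0.8560) = 1.034
- Strong: W = 0.3682, V = 0.0022; √(0.9150 / 0.7386) = 1.113

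Simulated ratios against the standardised logistic estimate agree: at N = 170, about 0.6% (none), 3–4% (moderate) and 7–14% (strong); at N = 60, about 2%, 4–5% and 9–14%. Other runs under similar assumptions gave about 1%, 4–7% and 11–14%.

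**4. Test behaviour.** Under no effect at N = 170, nominal 10%, the z-test rejected in 9.7–11.0% (none), 8.7–9.4% (moderate) and 7.2–7.7% (strong) of trials; the standardised logistic test in 10.2–11.3%. Power at N = 60, 45% versus 70%, z-test against standardised logistic: 62–65% against 65–68% (none), 63% against 68% (moderate), 62% against 73% (strong). At N = 170 with NDURE at 90% or more, both have power of about 100%.

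**5. How often the model fails.** Ranges run across the three stratum-effect settings. The first two result columns use ordinary iteratively reweighted least squares (400 runs per cell); the last uses a step-halving solver started from a valid interior point, counting a stop at the boundary as failure (800 runs).

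| N | Usual care / NDURE | Non-convergence only | Non-convergence or fitted value outside 0–1 | Step-halving solver, any failure |
|---|---|---|---|---|
| 170 | 45% / 70% | 0–1% | 0–5% | 0–4% |
| 170 | 50% / 80% | 0–5% | 1–23% | 1–23% |
| 170 | 50% / 90% | 5–15% | 10–61% | 10–68% |
| 170 | 60% / 95% | 9–15% | 34–66% | 42–91% |
| 60 | 45% / 70% | 2–7% | 4–29% | 3–33% |
| 60 | 50% / 80% | 5–11% | 13–44% | 19–58% |
| 60 | 50% / 90% | 11–13% | 43–56% | 52–88% |
| 60 | 60% / 95% | 6–11% | 50–62% | 80–95% |

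The definition of failure moves the answer as much as the rates do. The plan's literal trigger, non-convergence, occurs in about 0–15% of trials with the ordinary solver.

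**6. Limits of the better fallback.** At N = 60 with NDURE at 95%, logistic separation occurred in roughly 20–27% of simulated trials, so the logistic route also needs a last resort.

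**The case against.** The strongest reply is that the z-test is pre-specified, always computable and valid. It estimates the same population-average risk difference as Section 9.4.3.2 intends, and its rejection rate under no effect is about nominal or below. Where the model is most likely to fail at full sample size, power is about 100% either way. All of this stands; it limits the point to precision and consistency.

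A reader might infer that failure is likely because NDURE will push these rates close to 100%. The documents do not support that. They give no expected rate for any of the three endpoints; Section 6.1.1.1 speaks only of optimising adherence. Section 8.4.6 scores a patient as not having had the consultation if PORT is later given at another facility, which can hold that rate down. No size is given for the dental subsets, so N = 60 is only an illustration.

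It is also fair that race and facility are linked in Section 6.3 to PORT delay, not to dental care or consultation. With small additive effects (race 5 points, facility 10 points), the strata explain (2/9) × 0.05² + 0.25 × 0.10² = 0.0031 of an average outcome variance of about 0.15–0.18, or roughly 2%, and the SE penalty is about 1%.

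None of this explains why two rescue routes were written for one model.

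**Conclusion.** The inconsistency is in the current text and unexplained. Its consequence is a somewhat conservative test and wider intervals for three care-process endpoints. The SE is about 1% larger if the strata are not prognostic, about 4–7% if moderately and 11–14% if strongly prognostic, with some scenarios as low as about 3% and 7%. These sizes rest on assumed rates, facility split and stratum effects.

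The chance of using the fallback cannot be stated from the documents. It rises as NDURE rates approach 90–95%, in small subsets, and if out-of-range fitted values count as failure, which depends on software.

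Three stronger readings should be resisted: that the unadjusted comparison is biased, that failure is to be expected, and that all secondary binary analyses are affected (PORT delay disparity is not). The point is minor, and it does not touch the primary analysis.

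**What to change.** In Section 9.4.4.2, for all three endpoints:
- Replace the unadjusted fallback with the one in Section 9.4.3.2: a standardised risk difference from a logistic model with arm, race and predicted facility, with a 90% CI by delta method or bootstrap.
- Define failure of the identity-link model as non-convergence or any fitted probability outside 0–1, so that the choice does not depend on the software.
- Keep the unadjusted rates and z-test only as the last resort, when the logistic model shows separation.

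The cost is a few sentences. The method is already specified for the primary endpoint, and no data collection or sample size changes. This is a free improvement.
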